### Purpose of Study

Women who receive epidural analgesic during labor often experience hypotension, typically within the first 30 minutes after epidural placement. This maternal low blood pressure can impact blood flow to the infant which is seen through decreases in the infant's heart rate. The current study aims to evaluate whether elevating patients' legs on a peanut ball for the first 40 minutes after epidural placement will decrease the incidence of maternal hypotension and fetal heart rate decelerations.

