### Hypothesis or Research Question

- Hypothesis 1: Laboring women who receive epidural analgesia and elevate their legs on a peanut ball will experience a lower incidence of requiring intervention for low blood pressure compared to laboring women who receive epidural analgesia and do not elevate their legs.
- Hypothesis 2: Laboring women who receive epidural analgesia and elevate their legs on a peanut ball will experience a lower incidence of hypotension compared to laboring women who receive epidural analgesia and do not elevate their legs.  
\*hypotension is defined as SBP < 90 mmHg or an SBP decreases more than 20% from baseline
- Hypothesis 3: Infants of laboring women who receive epidural analgesia and elevate their legs on a peanut ball will experience a lower incidence of late or prolonged decelerations compared to laboring women who receive epidural analgesia and do not elevate their legs.

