## Background

Aortocaval compression (ACC) by the gravid uterus is a known physiological phenomenon that is claimed to cause supine hypotension in full term pregnant patients. ACC has been noted as a possible cause of post-spinal hypotension (PSH). Hypotension is defined as a systolic blood pressure of less than 90mmHg or a diastolic blood pressure of less than 60mmHg. The left tilt is the usual solution to remedy the hypotension for laboring women. Maternal physiologic changes such as increased blood volume has an impact on the circulation system: low maternal blood pressure can result in decreased perfusion of the placenta. This negatively impacts maternal blood flow to the fetus which is noted on the fetal monitor as a Category II or III fetal heart tracing. While hypotension may not cause problems in some women, the fetus in utero is accustomed to and dependent on a certain blood pressure threshold.

A peanut labor ball (PB) is a non-latex, plastic, air-filled yoga ball that is shaped like a peanut. It is used during labor for maternal pain relief and maternal position changes. The goal of using the PB is to shorten the duration of labor by keeping open the laboring woman's pelvic floor and to decrease the incidence of cesarean sections or medical -assisted vaginal deliveries, by the use of forceps and vacuums, among women who receive epidural anesthesia.

The purpose of this study is to examine the effectiveness of elevating a woman's legs on a PB in preventing hypotension among a sample of laboring women who receive an epidural analgesia.

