When a patient who meets the inclusion/exclusion criteria is admitted, a nurse will describe the study, answer any questions the patient has, and if the patient wants to enroll in the study, the study team nurse will review the information consent form. After the patient provides written informed consent, the nurse will remove the next envelope out of a box of prefilled and sealed opaque envelopes. The envelope will provide the Subject ID number to be used on all study-related documentation and the study Arm that the patient has been randomized to, either:

1. Leg Elevation Group
2. Standard Care Group

These envelopes will be filled using a computerized simple random number generator (1:1 randomization) prior to the start of the study.

In addition to the group assignment, the envelope will include a data collection form. Data will be recorded directly on this form during the patient's visit. The form will collect the following information:

- Whether patient was assigned to the leg elevation group or the standard care group
- Patient age
- Pregnancy history
- Height
- Weight
- Whether pregnancy is a singleton or multiple pregnancy
- Blood pressure documented at last prenatal office visit
- Threshold systolic blood pressure (20% decrease from office visit blood pressure) – The study team nurse will calculate threshold systolic blood pressure by calculating the systolic blood pressure from most recent office visit multiplied by 0.8
- Time of epidural placement
- Time legs elevated on peanut ball (Intervention group only)
- Time legs removed from peanut ball (Intervention group only)
- Did the infant have any late or prolonged decelerations within the 1 hour after epidural placement? Yes/No
- Did the RN have to perform any interventions to address prolonged or late decelerations during the 1 hour after epidural placement? Yes/No
- Did the anesthesia provider treat the maternal blood pressure during the 1 hour after epidural placement? Yes/No

RN will complete the data collection form and place the signed informed consent form and data collection form in a locked room designated for study materials.

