On the data collection forms, RNs are instructed to call a member of the study team immediately if there are any safety concerns related to the leg elevation. If the study team receives a call about a safety concern, recruitment and enrollment of new participants will stop until the study team meets and reviews the incident and determines it is safe to continue. Any adverse events and serious adverse events will be reported to the IRB in compliance with IRB safety policies.

- **Intervention or experimental aspect of the study**

After epidural placement, nurse will verify that patient received 1L of IV fluid and had Category I fetal heart tracing in the one hour prior to epidural placement. If

either of these aren't met, patient will be removed from study and no further procedures will take place.

If patient received 1L of IV fluid and had Category I fetal heart tracing in previous 1 hour, patients randomized to Arm 1 will be placed in a left tilt position with a hip wedge. Next both legs will be elevated on an orange peanut ball. the epidural placement. Their legs will be lowered approximately 40 minutes after after epidural placement. Peanut ball use during labor is a standard practice on this unit. The intervention will involve using the peanut ball for leg elevation

Patients randomized to Arm 2 will receive standard care. After epidural placement, they will be placed in a left tilt position with a hip wedge. Patient will remain in this position for 40 minutes after epidural placement.

After the 40 minutes of positioning or leg elevation, the next blood pressure obtained will be documented on the data collection form and then the study procedures are completed.

- **Statistical Analysis**

Data recorded on paper data collection forms will be entered into a password protected database. Only study team members will have access to the database. No personal information will be entered into the electronic database. Data will undergo range checks when entered into the database, and quality control procedures will be performed to ensure accuracy of the data in the electronic database.

Statistical analyses will be performed using Intellectus Statistics statistical software. The following analyses will be performed to address each hypothesis:

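### Hypothesis 2 (maternal hypotension) has no time window and no stated source readings, and the only post-epidural pressure the plan records falls after the expected risk period

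*Combined protocol and SAP*

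**What the plan says.** - **Threshold.** Under Hypothesis or Research Question, "hypotension is defined as SBP < 90 mmHg or an SBP decreases more than 20% from baseline".
- **Baseline.** The Data Collection list includes "Threshold systolic blood pressure (20% decrease from office visit blood pressure"), computed as the most recent office systolic pressure times 0.8. This implies that the office visit is the baseline.
- **Where data go.** "Data will be recorded directly on this form", and Statistical Analysis says the database is filled from the paper forms.
- **Outcome items with a window.** Decelerations, nurse intervention for decelerations, and anesthesia treatment are each Yes/No items over 1 hour. The last reads "Did the anesthesia provider treat the maternal blood pressure during the 1 hour after epidural placement".
- **Post-epidural pressure.** The intervention section has one: "After the 40 minutes of positioning or leg elevation, the next blood pressure obtained will be documented on the data collection form". Study procedures then end.
- **Timing.** The Purpose of Study says hypotension occurs "typically within the first 30 minutes after epidural placement". For Arm 1, "Their legs will be lowered approximately 40 minutes" after placement.
- **Use.** Statistical Analysis applies a chi-square test to whether hypotension occurred. It also makes hypotension one of two outcomes that can end data collection at an interim look.
- **A second definition.** Background says "Hypotension is defined as a systolic blood pressure of less than 90mmHg or a diastolic blood pressure of less than 60mmHg". This is a minor wording difference, but it should be reconciled with the Hypothesis 2 rule.

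**The concern.** Whether hypotension occurred is a question about an interval, and it needs a window and a set of readings. The plan states neither. A site that followed the text literally would hold, for each woman, one office pressure, one threshold derived from it, and one reading at an unspecified time after 40 minutes. Those data can show whether she was hypotensive at that moment. They cannot show whether she became hypotensive after the epidural.

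The late reading is also taken under different conditions in the two arms, since only Arm 1 has had a change in leg position just before it.

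At stake are the meaning of a named hypothesis and of an interim stopping criterion. Hypothesis 1, on which the sample size was based, and Hypothesis 3 have their own 1-hour form items and are not affected.

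**Working it through.** **1. Reproduce the reported result.** Results gives 13% of 54 versus 21% of 38, X²=1.07, p=0.30. The only whole counts that fit are 7/54 (13.0%) and 8/38 (21.1%); the neighbouring counts give 11.1% or 14.8%, and 18.4% or 23.7%. For the Pearson chi-square without continuity correction, a=7, b=47, c=8, d=30, N=92:

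X² = N(ad − bc)² / [(a+b)(c+d)(a+c)(b+d)]
= 92 × (210 − 376)² / (54 × 38 × 15 × 77)
= 2,535,152 / 2,370,060 = 1.07, p=0.301.

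The arithmetic is sound. It does not show which readings lie behind the 7 and the 8.

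**2. Compare how the three hypotheses are supplied with data.**

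| | Listed form item | Window | Source |
|---|---|---|---|
| H1, intervention for low pressure | Yes/No, anesthesia treatment | 1 hour from placement | Form |
| H2, hypotension | None | None stated | None stated; only the post-positioning reading is said to be documented |
| H3, decelerations | Yes/No | 1 hour from placement | Form |

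**3. Place the recorded reading in time.**

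- 0 to 30 minutes: hypotension typically occurs (Purpose of Study).
- 0 to about 40 minutes: positioning in both arms, with legs elevated in Arm 1.
- About 40 minutes: legs due to be lowered in Arm 1.
- After 40 minutes, at an unspecified time: the documented pressure.
- 60 minutes: end of the window for the other outcome items.

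The reading therefore comes at least 40 − 30 = 10 minutes after the period of expected hypotension.

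**4. Look for a window elsewhere.** The 40 minutes in the Purpose of Study is the duration of leg elevation, not an outcome window. The 1-hour wording belongs to the other three items. The anesthesia item records treatment, not a pressure against the threshold. The threshold field implies that some later reading is compared with it, but no reading, schedule or field is given. No chart review is named.

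**5. Consequence if the recorded data are used.** A woman whose pressure crossed the threshold in the first 30 minutes and recovered, with or without treatment, would be scored as not hypotensive. The direction of the resulting bias cannot be signed: treatment may differ between arms in a non-blinded trial, and only Arm 1 is measured after a change of leg position. The documents give no proportion of episodes still visible at the late reading, so no numerical correction follows.

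**The case against.** The strongest reply is that nothing says the late reading scores Hypothesis 2. The form itself is not in the documents, and the Data Collection list is plainly incomplete because it omits even the post-positioning reading. A pre-calculated threshold suits bedside checking of successive pressures, and a reported rate shows that the outcome was scored somehow. This stands. It limits what is established to an unstated outcome definition, with missed early episodes as a conditional consequence. It does not supply the missing window or source.

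A second reply is that enrolment has ended and results are reported, so new form items help only further enrolment or reuse. That is also right.

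Three stronger readings are tempting and are not supported:

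- A reader might infer that the 13% versus 21% came from the late reading. Results does not name the readings.
- A reader might infer that the non-significant result hides a real effect. That needs assumed numbers of missed episodes, which the documents do not give.
- A reader might take the significant Hypothesis 1 result as proof that treated hypotension went unscored. As reported, that outcome pools nurse or physician intervention for hypotension or for late decelerations, so it cannot show this.

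Nor do the documents say that hypotension triggered a stop. The reported p-values for the two stopping outcomes are 0.30 and 0.15.

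**Conclusion.** The point holds as a gap in outcome definition and should be fixed. Hypothesis 2 has a threshold and an implied baseline but no window and no source readings, and the same gap carries into the interim rule. This rests on the text alone.

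The bias is conditional on the outcome being scored from the one post-epidural pressure the plan says is recorded. On that assumption earlier treated or resolved drops are missed, by an unknown amount and in an unknown direction. If other readings were used, the bias may be absent, but the definition is still unstated. Until the readings are named, the reported comparison (7/54 versus 8/38) cannot be interpreted as a comparison of hypotension after epidural placement.

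**What to change.** **Plan text, for further enrolment or reuse.**

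- Define Hypothesis 2 as any systolic pressure meeting the stated rule, judged against the office-visit threshold on the form, from epidural placement to 60 minutes. This matches the window of the other outcome items.
- Add three form items in both arms: lowest systolic pressure, its time, and number of readings.
- Keep the post-positioning reading as descriptive.
- Use the same definition in the interim rule, and reconcile the Background definition with it.

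**For the 92 women already analysed.**

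- State which readings and window produced 13% versus 21%. This may settle the matter.
- If it was the late reading, either report the result as post-positioning blood pressure, or re-score from charted systolic pressures without knowledge of arm. Label any re-scoring post hoc and give the number of readings per arm.
- A cross-tabulation of the anesthesia item against hypotension status by arm is optional. It is only supportive, because a treated woman need not have crossed the threshold.

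**Cost and downsides.** The plan change is one sentence and three form items. Naming the readings should need no new data; re-scoring may need chart review. A lowest-value rule depends on how often pressure is charted, which may differ by arm in a non-blinded trial; hence the count of readings. Sixty minutes is a choice: it runs 60 − 40 = 20 minutes past positioning, and 40 minutes could also be defended. The window must be fixed before any scoring.

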## Research Plan

- **Study Design**

This study will use a randomized, non-blinded, controlled design with two arms:

- Arm 1 (Intervention): Immediately after epidural placement, patient will be placed in a left tilt position with her hip on a wedge and both of her legs elevated on an orange peanut ball. She will remain in this position for approximately 40 minutes.
- Arm 2 (Control/Standard Care): Immediately after epidural placement, patient will be placed in a left tilt position with her hip on a wedge. She will remain in this position for approximately 40 minutes.

- **Setting for the study**

The study will take place on Good Samaritan Hospital's Labor and Delivery Unit. This unit consists of 20 labor rooms and provides care to approximately 11 laboring women each day.

- **Participants**

The study will enroll 300 women who meet the following inclusion/exclusion criteria:

Inclusion Criteria:

- Laboring at Good Samaritan Hospital Labor & Delivery Unit
- 37+ weeks gestation
- Planned vaginal delivery
- Planned epidural analgesia

Exclusion Criteria:

- Under 18 years old
- Does not speak English
- Unable to consent to involvement in the research study
- Attended less than 3 prenatal care office visits
- Diagnosed with fetal demise
- Diagnosed with fetal anomalies
- Contraindications to both legs being elevated (ex: fractured bones, lower limb amputation, etc.)
- Contraindications to receiving 1L of IV fluids
- Requiring IV hypertensive medications
- Requiring IV magnesium

Sample Size Determination: A power analysis was conducted using a dichotomous outcome variable, requiring intervention for low blood pressure, with an expected difference [(33% incidence rate (Auroy et al., 1997), clinical significance would be a decrease to 15%)] (0.2), power of 0.8, and level of significance 0.05. It was determined that 120 patients would be needed in each group, for a total sample size of 240 patients. To allow us to also examine the impact on occurrence of infant decelerations and to allow for the possibility of removing participants from the final analysis due to missing data, we plan to enroll 300 patients (150 in each group).

- **Data Collection**

Before the study begins, information about the study will be provided to the nurses on the L&D unit including education about the study purpose, inclusion/exclusion criteria, and procedures.

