Hypothesis 1: Laboring women who receive epidural analgesia and elevate their legs on a peanut ball will experience a lower incidence of requiring intervention for low blood pressure compared to laboring women who receive epidural analgesia and do not elevate their legs.

*To compare the effects of leg elevation, a Chi Square test will be used to compare occurrence of receiving intervention for low blood pressure for patients who elevated their legs to patients who did not elevate their legs. A level of significance of  $\alpha=0.05$  will be used.*

Hypothesis 2: Laboring women who receive epidural analgesia and elevate their legs on a peanut ball will experience a lower incidence of hypotension compared to laboring women who receive epidural analgesia and do not elevate their legs.

*To compare the effects of leg elevation, a Chi Square test will be used to compare occurrence of maternal hypotension for patients who elevated their legs to*

*patients who did not elevate their legs. A level of significance of  $\alpha=0.05$  will be used.*

Hypothesis 3: Infants of laboring women who receive epidural analgesia and elevate their legs on a peanut ball will experience a lower incidence of late or prolonged decelerations compared to laboring women who receive epidural analgesia and do not elevate their legs.

*To compare the effects of leg elevation, a Chi Square test will be used to compare occurrence of late or prolonged infant decelerations for patients who elevated their legs to patients who did not elevate their legs. A level of significance of  $\alpha=0.05$  will be used.*

Interim data analysis will occur (1) once approximately 1/3 of the participants have been enrolled and (2) once approximately 2/3 of the participants have been enrolled. If interim calculations at time (1) or time (2) note a significant difference between groups in maternal hypotension or frequency of late or prolonged fetal decelerations, data collection will be completed at that time and final analysis will be completed.

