**Hypothesis 1:**

There is a significantly lower frequency of requiring RN or MD intervention for hypotension or late decelerations among patients in the intervention group (11%) compared to patients in the control group (29%),  $X^2 = 4.71$ ,  $p=0.03$ .

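### Three hypotheses are each tested at 0.05 with no stated primary, order or adjustment; the one nominal hit (p=0.030, on an outcome wider than planned H1) does not survive Holm (0.090)

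*Combined protocol and SAP*

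**What the plan says.** Under Statistical Analysis in the Research Plan, each hypothesis has its own test.

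- H1: "To compare the effects of leg elevation, a Chi Square test will be used to compare occurrence of receiving intervention for low blood pressure".
- H2: "a Chi Square test will be used to compare occurrence of maternal hypotension".
- H3: "a Chi Square test will be used to compare occurrence of late or prolonged infant decelerations".

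The sentence "A level of significance of $\alpha=0.05$ will be used" follows each of the three. No section names a primary outcome, ranks the hypotheses or adjusts for testing three.

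The sections differ on which outcome leads.

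- Sample Size Determination: "A power analysis was conducted using a dichotomous outcome variable, requiring intervention for low blood pressure". This is H1.
- Purpose of Study asks whether leg elevation "will decrease the incidence of maternal hypotension and fetal heart rate decelerations". These are H2 and H3.
- Background gives the purpose as preventing hypotension. This is H2.
- The interim rule at the end of Statistical Analysis stops data collection on a significant difference in hypotension or in decelerations. These are H2 and H3, not H1.

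The Results section gives one verdict per hypothesis. For H1 it says "There is a significantly lower frequency of requiring RN or MD intervention for hypotension or late decelerations among patients in the intervention group (11" and continues with 11% against 29% and p=0.03. H2 (13% against 21%, p=0.30) and H3 (19% against 32%, p=0.15) are reported as not significant.

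**The concern.** When three tests each run at 0.05 and nothing ranks them, any one success can be called significant. The 5% level then describes each test separately. It does not describe the statement that leg elevation helps on at least one of the outcomes.

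This matters here because exactly one of the three tests crossed 0.05, and only modestly. A reader of the Results is told that this difference is significant, and is not told that it is one unadjusted result among three.

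**Working it through.** **Inputs.** The level is 0.05 for each of three tests (Statistical Analysis). The analysed numbers are 54 and 38 (Results). The percentages and chi-squares are those reported under each hypothesis. The correlation between outcomes is not given, so it is an assumption and is varied.

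**Step 1: reproduce the reported results.** Only one pair of counts matches each pair of rounded percentages. The uncorrected Pearson chi-square is N(ad − bc)² / (product of the four margins).

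| | Leg elevation | Standard care | Chi-square | p |
|---|---|---|---|---|
| H1 as reported | 6/54 | 11/38 | 92 × (6×27 − 48×11)² / (54×38×17×75) = 4.71 | 0.030 |
| H2 | 7/54 | 8/38 | 92 × (7×30 − 47×8)² / (54×38×15×77) = 1.07 | 0.301 |
| H3 | 10/54 | 12/38 | 92 × (10×26 − 44×12)² / (54×38×22×70) = 2.09 | 0.148 |

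All three agree with the document.

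**Step 2: chance of at least one rejection when all three nulls are true, at a single final look.**

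- Upper bound: 3 × 0.05 = 15%.
- Independent tests: 1 − 0.95³ = 14.3%.
- Equally correlated normal test statistics, simulated: 13.6% at correlation 0.3, 12.5% at 0.5, 10.9% at 0.7 and 9.8% at 0.8.
- Lowest value the reported counts allow: with pooled counts of 17, 15 and 22 out of 92, the largest possible correlation between two binary outcomes with counts a ≤ b is √[a(92 − b) / ((92 − a)b)]. This gives 0.93 (H1 with H2), 0.85 (H1 with H3) and 0.79 (H2 with H3). Simulation with these values gives about 9%.

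The range is therefore about 9-15%.

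**Step 3: benefit direction only.** All three hypotheses predict a lower incidence, so a false claim of benefit needs a rejection in that direction. One two-sided test at 0.05 gives 2.5%. Three independent tests give 1 − 0.975³ = 7.3%. At correlation 0.7 the simulated figure is 5.5%, and at the limit in Step 2 it is about half of 9%, or 4.5%. In round terms this is 5-7%.

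**Step 4: Holm on the reported p-values.** Ordered, they are 0.030 (H1), 0.148 (H3) and 0.301 (H2).

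- H1: 3 × 0.030 = 0.090.
- H3: 2 × 0.1482 = 0.296.
- H2: 1 × 0.301 = 0.301.

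None is below 0.05.

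**Step 5: compare planned and reported H1.** The plan is to "compare occurrence of receiving intervention for low blood pressure for patients who elevated their legs to patients who did not elevate their legs". The Results count RN or MD intervention for hypotension or for late decelerations, which is a wider event. The p-value of 0.030 is therefore not a test of H1 as planned, and no result for planned H1 is reported.

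**The case against.** The strongest reply is that H1 is in effect the primary outcome. It is listed first and is the only outcome in the power calculation. The sample size paragraph also treats decelerations as something the larger enrolment allows the study to examine in addition. On that reading a test of H1 at 0.05 needs no adjustment for H2 and H3. This is a fair reading, so a flat statement that H1 was unprotected would go too far. It does not close the point, for two reasons. The purpose and the stopping rule give the leading place to H2 and H3. And an implicit primary could protect only intervention for low blood pressure, not the wider event that was reported.

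A second reply is that the 9-15% includes false findings of harm and depends on an assumed correlation. Both parts stand. The outcomes overlap, since treating low blood pressure largely presupposes low blood pressure, so values below the independent-tests figure are likely. For claims of benefit the relevant range is about 5-7%, which is still two to three times 2.5%.

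A reader might also infer that the one favourable result was picked out as the trial's positive finding. The documents do not support that. The Results state all three outcomes in parallel, report the two null results plainly, and draw no overall conclusion.

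**Conclusion.** The plan does not control error across its three hypotheses, and it leaves the primary outcome ambiguous. With all nulls true and one final look, at least one nominally significant result is expected in about 9-15% of such trials, and a false claim of benefit in about 5-7%. Both ranges assume a correlation structure that the documents do not give. They exclude the two interim looks, which are a separate source of error.

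The H1 result is best read as nominal: p=0.030 unadjusted, 0.090 under Holm, for an outcome that differs from the planned one. It would be too strong to infer that leg elevation has no effect, or that H1 as planned failed. Failing Holm shows neither, and planned H1 has not been reported.

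**What to change.** **Plan, had it been changed before the data were seen.** One sentence was enough: H1, as defined under Hypothesis or Research Question, is the single primary outcome at two-sided 0.05. H2 and then H3 are tested in that order, and once one fails the later ones are descriptive.

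**Now that results are known.** A primary named today would not be prespecified, so none should be named. In the Results:

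1. Show the Holm-adjusted p-values beside the raw ones: 0.090 (H1 as reported), 0.301 (H2) and 0.296 (H3).
2. Describe the H1 result as nominal and exploratory, and remove the wording that calls it significantly lower.
3. Report the result for H1 as planned. The data collection form records whether the anesthesia provider treated maternal blood pressure within one hour of epidural placement. If this result replaces the wider event in the set of three, recompute the Holm values.

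The cost is three adjusted p-values, one reworded sentence and one additional comparison from data already collected. The downside is that the H1 statement becomes less favourable.

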**Hypothesis 2:**

There is no significant difference in frequency of low blood pressure among patients in the intervention group (13%) compared to patients in the control group (21%),  $X^2 = 1.07$ ,  $p=0.30$ .

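### Each hypothesis is planned as a bare chi-square, with no risk difference or confidence interval and no use of the recorded office blood pressure as a covariate; reporting both would be a cheap improvement

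*Combined protocol and SAP*

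**What the plan says.** The Statistical Analysis part of the Research Plan gives one test per hypothesis, each at a 0.05 level:

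- Hypothesis 1: "a Chi Square test will be used to compare occurrence of receiving intervention for low blood pressure"
- Hypothesis 2: "a Chi Square test will be used to compare occurrence of maternal hypotension"
- Hypothesis 3: "a Chi Square test will be used to compare occurrence of late or prolonged infant decelerations"

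No risk difference, ratio, confidence interval or covariate is mentioned.

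The Data Collection part lists as a form item "Blood pressure documented at last prenatal office visit". A second item is each woman's threshold, defined as "systolic blood pressure from most recent office visit multiplied by 0.8". Office systolic pressure (SBP) therefore feeds the 20%-fall part of the hypotension definition but enters no model. Allocation is by simple 1:1 randomization, with no stratification stated.

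The Results section reports both arm percentages, the chi-square and the p-value for each hypothesis. Hypothesis 2 is worded "There is no significant difference in frequency of low blood pressure", and Hypothesis 3 is worded in the same way. The Demographics table covers age, height and weight, and a sentence below it adds plurality and pregnancy history. Office blood pressure appears in neither.

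**The concern.** A chi-square with a p-value says whether the data are surprising under no effect. It does not say which effects remain compatible with the data. The trial planned 300 women and analysed 92, so a statement of no significant difference is easily read as evidence of no effect. An interval would guard against that reading.

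Office SBP is a reasonable covariate for the maternal outcomes. It is measured before randomization, it sets the personal threshold, and it should be available for most women because those with fewer than 3 prenatal visits are excluded. Since it is missing from the baseline table, a reader cannot see whether it happened to differ between arms. At stake are how Hypotheses 2 and 3 may be described and, less certainly, some precision.

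**Working it through.** **1. Rebuild the counts and reproduce the reported statistics.** The denominators are the women who completed the study, 54 and 38, assumed to apply to all three outcomes. For each hypothesis only one pair of whole numbers matches the rounded percentages. With events a and c, non-events b and d, X² = N(ad − bc)² / (product of the four margins):

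- Reported under H1, 6/54 vs 11/38: 92 × (6×27 − 48×11)² / (54×38×17×75) = 92 × 366² / 2,616,300 = 4.71, p = 0.030.
- H2, 7/54 vs 8/38: 92 × 166² / (54×38×15×77) = 1.07, p = 0.301.
- H3, 10/54 vs 12/38: 92 × 268² / (54×38×22×70) = 2.09, p = 0.148.

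All three agree with the Results section (4.71, 1.07, 2.09), as Pearson tests without continuity correction.

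**2. Risk differences with Newcombe 95% intervals.** With d = p1 − p2 and Wilson limits (l, u) for each arm, lower = d − √[(p1 − l1)² + (u2 − p2)²] and upper = d + √[(u1 − p1)² + (p2 − l2)²].

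| Outcome | Leg elevation, % (Wilson) | Standard care, % (Wilson) | Difference, points (95% CI) |
|---|---|---|---|
| Reported under H1 | 11.1 (5.2 to 22.2) | 28.9 (17.0 to 44.8) | -17.8 (-34.7 to -1.5) |
| H2 | 13.0 (6.4 to 24.4) | 21.1 (11.1 to 36.3) | -8.1 (-24.7 to +7.1) |
| H3 | 18.5 (10.4 to 30.8) | 31.6 (19.1 to 47.5) | -13.1 (-30.9 to +4.5) |

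For H2, for example: -8.09 − √(6.54² + 15.30²) = -24.7, and -8.09 + √(11.46² + 9.98²) = +7.1.

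**3. What adjustment could gain.** The documents give no association between office SBP and any outcome, so its strength is an assumption. One simulation used the planning rates of 33% and 15%, a logistic model with a standardised risk difference, and 3,000 replicates. It gave these ratios of unadjusted to adjusted variance:

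| Assumed odds ratio per SD of office SBP | N = 300 | N = 92 |
|---|---|---|
| 1.35 | 1.02 | 1.00 |
| 1.65 | 1.04 | 1.03 |
| 2.2 | 1.09 | 1.08 |
| 2.7 | 1.19 | 1.16 |

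A second simulation at 54 and 38 women (1,500 runs) found no gain at odds ratios of 1.0 to 1.3, and variance lower by about 2% at 1.5, 6% at 2.0 and 19% at 3.0.

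**4. Could it change the reading of H2 or H3?** Suppose 20% of the variance were removed and the estimates stayed where they are. Wald intervals then shrink by √0.8 = 0.894, to -22.2 to +6.0 points for H2 and -29.2 to +3.1 for H3. Both still include zero.

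**5. Is a linear term safe for H2?** Hypotension is SBP below 90 mmHg or a fall of more than 20%. The two limits meet at 90/0.8 = 112.5 mmHg: below that office SBP the fixed limit governs, above it the personal threshold does. An illustration assumed office SBP with mean 118 and SD 12, residual SD 12 and 20% events. The odds ratio per SD of office SBP was 3.1 if post-epidural SBP does not track office SBP, 1.07 if it tracks with slope 0.5, and 0.58 with slope 0.8. At slope 0.5 the risk was U-shaped: 25% in the lowest fifth, 14% in the second and 27% in the highest.

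**The case against.** The strongest reply is that nothing here is wrong. An unadjusted chi-square is valid in a randomized trial, and its error rate already allows for chance imbalance under simple randomization. That stands. A reader might infer that the planned tests are biased or invalid; the documents give no support for that.

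A reader might also infer that precision has demonstrably been lost. That is not shown. Every figure for the gain rests on an assumed association, and for H2 the association could be near zero on a linear scale, U-shaped or reversed. Nothing in the documents links office SBP to fetal decelerations, so adjustment has no stated basis for H3.

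Nor do the results say only that there is no significant difference. They give percentages, chi-squares and p-values, and the intervals above were derived from those. The plan still should not leave that derivation to the reader.

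Finally, the results are known. Choosing a covariate now is post hoc, and it would sit beside a fragile result: the comparison reported under H1 has p = 0.030 uncorrected, but Fisher's exact test gives 0.054. This stands as well and limits what adjustment may be called for this trial.

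**Conclusion.** The point holds as an inexpensive improvement in analysis and reporting. Its firmer half is the missing effect estimate and interval. H2 and H3 are inconclusive because their intervals run from falls of about 25 and 31 points to rises of about 7 and 4.5 points.

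It is tempting to add that both intervals contain the 18-point fall (33% to 15%) in the sample-size paragraph. That target is set only for requiring intervention for low blood pressure, and the documents set none for H2 or H3, so the intervals must speak for themselves. It is equally tempting to read -17.8 points as the planned H1 effect. The reported outcome combines RN or MD intervention for hypotension or late decelerations, whereas the planned one is intervention for low blood pressure.

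The adjustment half is softer. The variance gain is nil if office SBP is weakly related to the outcome, about 2 to 9% for assumed odds ratios of 1.35 to 2.2 per SD, and up to about 19% for stronger association. It would not be expected to change the H2 or H3 reading. With 92 of 300 planned women, sample size limits precision far more than the lack of a covariate. The intervals rest on the reconstructed counts and on denominators of 54 and 38.

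**What to change.** 1. For every hypothesis, report the risk difference with a 95% CI beside the chi-square. Label the H1 figure as the reported composite, and give the planned H1 outcome separately.
2. Word H2 and H3 as inconclusive, citing the intervals and not the 18-point target.
3. Add office SBP by arm, with the number of women who have it recorded, to the baseline table.
4. For the two maternal outcomes (H1 as planned, and H2), add to the plan a logistic model with assigned arm and continuous office SBP, allowing a non-linear term, and report the standardised risk difference with 95% CI. Do not extend it to H3.
5. For the results in hand, keep the chi-square as the stated test and label the adjusted estimate supportive and post hoc. With 15 hypotension events, a model with arm and two SBP terms is sparse (15/3 = 5 events per term), so its estimate needs cautious reading.

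The cost is a few sentences and routine analysis, with no new data collection and no more patients. The downsides are slightly more work and, for the existing results, a covariate chosen after the data were seen.
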